### 729 **Randomization**

730 Treatment assignment will occur at the second visit. The study statistician will generate a  
731 blocked randomization scheme (1:1) stratified by “any insulin treatment at time of  
732 screening” (yes/no) and BMI (cutoff 37 kg/m^2 – the average BMI of this study  
733 population in our PHHS Diabetes Clinic), programmed using SAS Proc Plan.

734

### 735 **Statistical Analysis Plan**

736 All statistical analyses will be performed by the study statistician ([name]), who  
737 has extensive experience in clinical trials analysis.

738 Primary analysis: The primary analysis will be intention-to-treat (ITT) which will include  
739 all randomized participants who receive at least one dose of a study medication. The  
740 non-inferiority of liraglutide treatment strategy compared to standard basal-bolus insulin  
741 regimen will be assessed using a 95% confidence interval for the between treatment  
742 group net difference (month 6 minus month 0) in HbA1c at 6 months. This 95%  
743 confidence interval will be derived from the differences of least square means estimated  
744 from a mixed model repeated measures analysis. Non-inferiority of liraglutide treatment  
745 will be concluded if the upper limit of the 95% confidence interval is less than the non-  
746 inferiority margin of 0.4%.

747

748 Secondary analyses: We will also perform a per-protocol analysis comparing HbA1c  
749 response because, in non-inferiority hypothesis testing, the ITT analysis may be biased  
750 toward the null hypothesis. The per-protocol population is defined as the population who  
751 continued the assigned intervention as randomized for the duration of the study period.  
752 Secondary outcomes include the composite endpoint of HbA1c<7% with no  
753 hypoglycemia and no significant weight gain, a binary variable, which will be compared  
754 between the randomized study groups with a logistic regression model. The odds ratio  
755 and corresponding 95% confidence intervals will be reported. From healthcare related  
756 cost data, cost-effectiveness ratios will be summarized as point estimates with 95%  
757 confidence intervals, accounting for the skewness in the distribution of the ratio[50].  
758 Sensitivity cost analyses will be performed to further assess variables such as treatment  
759 failure and quality of life weights. Multiple logistic regression models will be constructed  
760 to evaluate any association of baseline covariates on treatment efficacy. Binary  
761 secondary endpoints will also be assessed with logistic regression models. Group  
762 comparisons and changes from baseline over time (study visits) of continuous secondary  
763 outcome variables will be analysed with mixed model repeated analysis. The logrank test  
764 will be used to compare the pre-specified “treatment failure” end-point between groups.  
765 Safety endpoints and hypoglycemic and other adverse events will summarize in detail  
766 with descriptive statistics. The analysis of safety data will be performed for the ITT  
767 population.

768 Model assumptions regarding normality and covariance structure will be carefully  
769 assessed. Nonparametric tests or data transformations will be used if necessary to meet  
770 assumptions. Statistical analysis will be performed with SAS software (SAS Institute,  
771 Cary NC), particularly Proc Mixed for linear models with both fixed and random effects.

772 A two-sided alpha <5% will be considered significant for all analyses.

773

774 **Interim Analysis**

775 No interim analysis is planned.

776

777 **DATA HANDLING AND RECORD KEEPING:**

778 All data will be collected in strict compliance with the University's HIPPA rules.

779 Research records (source documents) will be kept in a double-locked filing system in a  
780 secure locked room. Collected data will be stored in an electronic study database will be  
781 encrypted and password protected and saved on the University's secure network. Only  
782 study personnel will have access to these records.

783

784 The institutional review board (IRB) governing this study may inspect the medical  
785 records of any patient involved in this study at any time.

786

787 Laboratory specimens will be collected under standard of care protocol at Parkland  
788 hospital laboratory and handled in accordance with the hospital policy.

789

790 The study blind will be maintained by the designated statistician and only broken by  
791 request from a treating physician in case of a medical emergency.

792

793 **ETHICS:**

794 Ethical Considerations:

795 1. Exclusion of non-English speakers- while translators are available during working  
796 hours, the investigators are worried that no translator will be available to assure  
797 safety measures at all times.

798 2. Compliance with Insulin Regimen- At times patients are not compliant with  
799 complicated insulin regimens and providers often continue to uptitrate insulin  
800 dosage when patients remain above HbA1c goal. If patient compliance improves  
801 once enrolled in the study, there is a higher risk of hypoglycemia. Every effort  
802 will be made at all visits to determine exactly what amount of insulin the patient  
803 is taking and the overall compliance.

804

805 Informed Consent:

806 Informed consent will be obtained during the first face-to-face contact. Once a  
807 prospective subject is identified, we will explain the study details and preliminary  
808 eligibility is accessed either through phone or face-to-face interview. If the prospective  
809 volunteer remains interested in the study and fulfils preliminary eligibility criteria,  
810 baseline studies are scheduled. Only study personnel listed on the consent will be  
811 permitted to obtain consent. The subject will be provided informed consent and it will be  
812 signed and witnessed. The consent form will discuss the procedures to be performed at  
813 each visit, the number of visits, and what is expected of the patient, along with all  
814 possible side effects. A copy will be given to the subject and the original will be kept on  
815 file. Potential subjects may be screened for eligibility using a study-specific HIPAA  
816 waiver. Volunteers who call to inquire about the study will have their demographic and  
817 contact information collected over the phone, and the study will be described to them.

818 Once the subject has agreed to participate and appears in person, a study specific HIPAA  
819 Authorization will be signed, along with the consent form document.

820

821 Confidentiality/HIPAA:

822 Every effort will be made to keep all information about the patient confidential. Consent  
823 forms will be placed in the patient charts. Research records will be kept in a double-  
824 locked filing system in a secure locked room. The electronic study database will be  
825 encrypted and password protected and saved on the University's secure network. Only  
826 study personnel will have access to these records.

827

828 The institutional review board (IRB) governing this study may inspect the medical  
829 records of any patient involved in this study.

830

831 IRB Approval:

832 The study is approved by the UT Southwestern IRB.

833

834 FDA Approval:

835 An IND/NDA exception was granted by the FDA for possible use of rescue therapy with  
836 prandial insulin add-on to detemir-liraglutide combination should patients in the  
837 liraglutide arm reach the pre-defined failure end-point.

838

839 Declarations:

840 This study will be conducted in accordance with the Declaration of Helsinki.

841 This study will be conducted in accordance with the ICH GCP guidelines.

842 The sponsor-investigator will comply with all applicable regulatory and legal  
843 requirements, ICH GCP guidelines, and the Declaration of Helsinki in obtaining and  
844 documenting informed consent.

845

846 Study schedule:

847 IRB approval: December 2013

848 Start of Study: as soon as funding received (estimate March 2014)

849 Recruitment period: March 2014 – February 2015

850 First Patient First Visit: March 2014

851 Last Patient First Visit: February 2015

852 Last Patient Last Visit: August 2015

853 Final Report: October 2015

854 Final Manuscripts: December 2015

855

856 **STUDY DRUGS AND MATERIALS:**

857 **Study medication**

858 Liraglutide 6 mg/ml solution for subcutaneous injection delivered in a 3 ml prefilled  
859 disposable pen

860 Detemir insulin 300 units/prefilled disposable pen

861 Aspart insulin 300 units/prefilled disposable pen

862

863 Provided and manufactured by NovoNordisk A/S.

864  
865 NovoFine Pen needles – provided by NovoNordisk US.  
866

867 **Storage and Drug Accountability of Study Medication(s)**

868 Patients will be instructed as follows:

- 869 -Store unused pens in a refrigerator at a temperature between +2°C and + 8°C
- 870 (36°F to 46°F). Keep away from the cooling element. Do not freeze and do not
- 871 use if it has been frozen.
- 872 -Store pens in use for 30 days at room temperature (15°C to 30°C; 59°F to 86°F)
- 873 or in a refrigerator (2°C-8°C; 36°F to 46°F).
- 874 -Do not freeze and do not use if it has been frozen.
- 875 -The pen must be protected from all sources of light, and the pen cap should be
- 876 kept on when the pen is not in use.
- 877 -Product should not be used if it does not appear clear and colorless.

878 Investigator will ensure availability of proper storage conditions and record and evaluate  
879 the temperature. While at the site, drug will be stored in a temperature-monitored  
880 refrigerator at 4°C.

881 There will be no trial medication dispensed to any person not enrolled in the study.

882 Unused medication will be stored separately from used trial medication(s).

883 Procedures for Drug Accountability:

- 884 -At study site all trial products will be kept in locked refrigerator and counted at
- 885 regular intervals
- 886 -At study site only enough medication will be dispensed to reach next
- 887 appointment. All medication will be counted at visits and discussed at phone
- 888 encounters.

889 Procedure for return of used/unused trial products:

- 890 -Unused product will be properly destroyed at the site or returned to sponsor if
- 891 requested.

892

893 **Auxiliary Supply**

894 Subjects will use their own glucose monitors, lancet devices, and lancets. They will be  
895 provided with log books.

896 **Randomization**

897 Treatment assignment will be made using stratified blocked randomization at visit 2. The  
898 stratification variables will be prior insulin use and BMI (cut off 37 kg/m^2). The  
899 randomization code will be generated by the study statistician using SAS software, and  
900 consecutively numbered envelopes will be created. The investigator opens the next  
901 envelope at the randomization visit to determine the group assignment of the patient.

902

903 **Blinding**

904 This study is only blinded to the investigator performing the study assessments. The  
905 study is not blinded to the patient, nor the study doctor who will be providing diabetes  
906 care to the patient and aid in insulin titration.

907

908 **CONCOMITANT ILLNESSES AND MEDICATIONS:**

909 **Definitions:**

910 Concomitant illness: any illness that is present at the start of the trial (*i.e. at the first*  
911 *visit*).  
912 Concomitant medication: any medication other than the trial product(s) that is taken  
913 during the trial, including the screening and run-in periods.  
914 Details of all concomitant illnesses and medication will be recorded at trial entry (*i.e. at*  
915 *the first visit*). Any changes in concomitant medication will be recorded at each visit. If  
916 the change influences the subject's eligibility to continue in the trial, the Sponsor will be  
917 informed.  
918 The information collected for each concomitant medication will include, at a minimum,  
919 start date, stop date or continuing, and indication.  
920 For each concomitant illness, date of onset, date of resolution or continuing, at a  
921 minimum, will be recorded.

922  
923 **ADVERSE EVENTS AND PREGNANCY:**

924 During each contact (phone or face-to-face) the subject will be asked about adverse  
925 events. All serious adverse events (SAE), suspected unexpected serious adverse  
926 reactions (SUSAR), and serious adverse drug reactions (SADR) will be evaluated by the  
927 investigator and recorded in the patients record. Other adverse events (AE) will be  
928 evaluated and documented according to standard clinical practice  
929 The sponsor-investigator will collect the following information at minimum for each of  
930 these events:

- 931 1. Study name
- 932 2. Patient identification (e.g. initials, sex, age)
- 933 3. Event (preferably a diagnosis)
- 934 4. Drug
- 935 5. Reporter identification (e.g. Name, or initials)
- 936 6. Causality
- 937 7. Outcome.

938

939 **Definitions**

940

941 **Adverse Event (AE):**

942 An AE is any undesirable medical event occurring to a subject in a clinical trial, whether  
943 or not related to the trial product(s). This includes events reported from the first trial  
944 related activity after the subject has signed the informed consent and until post treatment  
945 follow-up period as defined in the protocol. The following should not be recorded as  
946 AEs, if recorded as medical history/concomitant illness on the CRF at screening:

- 947 • Pre-planned procedure, unless the condition for which the procedure was planned has  
948 worsened from the first trial related activity after the subject has signed the informed  
949 consent
- 950 • Pre-existing conditions found as a result of screening procedures

951

952 **Clinical Laboratory Adverse Event:**

953 A clinical laboratory AE is any clinical laboratory abnormality regarded as clinically  
954 significant *i.e.* an abnormality that suggests a disease and/or organ toxicity and is of a

955 severity, which requires active management, (i.e. change of dose, discontinuation of trial  
956 product, more frequent follow-up or diagnostic investigation).

957

958 **Serious Adverse Event (SAE):**

959 A serious AE is an experience that at any dose results in any of the following:

960

- Death

961

- A life-threatening\* experience

962

- In-patient hospitalisation or prolongation of existing hospitalization

963

- A persistent or significant disability/incapacity

964

- • A congenital anomaly/birth defect  
965 Suspicion of transmission of infectious agents via  
the product.

966

- Important medical events that may not result in death, be life-threatening\*, or require  
967 hospitalization may be considered an SAE when, based upon appropriate medical  
968 judgement, they may jeopardise the subject and may require medical or surgical  
969 intervention to prevent one of the outcomes listed in this definition

970

\*The term life-threatening in the definition of SAE refers to an event in which the subject was at risk of  
971 death at the time of the event. It does not refer to an event which hypothetically might have caused death if  
972 it was more severe.

973

974 **Serious Adverse Drug Reaction (SADR):**

975

An adverse drug reaction (ADR) is an adverse event for which a causal relationship  
976 (Possible/Probable relation) between the study drug and the occurrence of the event is  
977 suspected. The ADR should be classified as **serious** if it meets one or more of the  
978 seriousness criteria. Clinical judgement following thorough review of any event will be  
979 used to determine the relatedness of the event to the study drug. .

980

981

982 **Non-Serious Adverse Event:**

983

A non-serious AE is any AE which does not fulfil the definition of an SAE.

984

985 **Severity Assessment Definitions:**

986

- Mild: Transient symptoms, no interference with the subject's daily activities

987

- Moderate: Marked symptoms, moderate interference with the subject's daily activities

988

- Severe: Considerable interference with the subject's daily activities, unacceptable

989

990 **Relationship to study medication Assessment Definitions:**

991

- Probable: Good reasons and sufficient documentation to assume a causal relationship

992

- Possible: A causal relationship is conceivable and cannot be dismissed

993

- Unlikely: The event is most likely related to an etiology other than the trial product

994

995 **Outcome Categories and Definitions:**

996

- Recovered: Fully recovered or by medical or surgical treatment the condition has  
997 returned to the level observed at the first trial related activity after the subject signed the  
998 informed consent

999

- Recovering: The condition is improving and the subject is expected to recover from the  
1000 event. This term should only be used when the subject has completed the trial

- 1001 • Recovered with sequelae: As a result of the AE, the subject suffered persistent and
- 1002 significant disability/incapacity (e.g. became blind, deaf, paralysed). Any AE recovered
- 1003 with sequelae should be rated as an SAE
- 1004 • Not recovered
- 1005 • Fatal
- 1006 • Unknown

1007

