#### 401 *Screening Visit (visit 1):*

402 During the screening visit patients will complete the informed consent process and will  
403 undergo a complete assessment for all inclusion and exclusion criteria. A complete  
404 medical history and comprehensive physical examination will be performed. Blood will  
405 be drawn (if not done within the past 7 days) to assess for all eligibility criteria (HbA1c,  
406 creatinine, liver function tests and pregnancy test, if applicable). Patients will receive an  
407 identification card with information about participation in the study. Patients will be  
408 asked to complete a 7-point glucose profile on the day prior to their next visit.  
409

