#### 410 *Randomization (visit 2):*

411 Randomization will occur at the second visit (3-7 days from visit 1-screening). The study  
412 statistician will generate a blocked randomization scheme (1:1) stratified by "any insulin  
413 treatment at time of screening" (yes/no) and BMI (cutoff 37 kg/m^2 – the average BMI of  
414 this study population in our PHHS Diabetes Clinic).  
415

416 At this visit we will obtain a full baseline evaluation of all outcome parameters. All  
417 patients will meet with the dietician to received education regarding recommended  
418 lifestyle modifications. Patient will undergo diabetes education as well as teaching  
419 regarding insulin injection and titration.  
420

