 457 meals taken daily. Meal-time insulin titration, if needed, can be either patient driven (see  
 458 table below) or physician-directed during the scheduled follow-up visits (phone or in  
 459 person), as well as any unscheduled patient-initiated visits (if applicable).

460

461 Novolog patient self-titration table:

Glucose prior to lunch	Change in breakfast insulin dose	Glucose prior to dinner	Change in lunch insulin dose	Glucose prior to bedtime	Change in dinner insulin dose
<54	-2 units	<54	-2 units	<54	-2 units
55-69	-1 unit	55-69	-1 unit	55-69	-1 unit
70-120	No change	70-120	No change	70-130	No change
121-160	+1 unit	121-160	+1 unit	131-180	+1 unit

>160	+2 units	>160	+2 units	>180	+2 units
------	----------	------	----------	------	----------

462

463 **Rescue therapy:**

464 Should any patients randomized to liraglutide treatment experience persistent  
465 hyperglycemia (defined as a confirmed Hb1c>10%) at the 3-mo visit (visit 5), meal-time  
466 insulin aspart will be initiated per the same protocol as above. This is a pre-specified  
467 “treatment failure” end-point. Following initiation of rescue therapy patients will  
468 continue all scheduled visits and procedures through the end of the trial.

469

470 Should any patients randomized to the “standard of care” group experience persistent  
471 hyperglycemia (defined as a confirmed HbA1c >10%) at the 3-mo visit (visit 5),  
472 treatment and insulin titration will continue as scheduled. This is also a pre-specified  
473 “treatment failure” end-point.

474

475 A graphical review of the visit procedures and timing is presented below:

Visit	1	2	3	4	5	6
Time	3-7	0	2 weeks	1	3	6
Type	Office	Office	Phone	Office	Office	Office
Consent	x					
I&E criteria	x					
Randomization criteria		x				
Randomization		x				
Physical exam	x			x	x	x
Height	x					
Vitals (weight, BP, pulse)	x	x		x	x	x
Dietary counseling	x	x	x	x	x	x
Lifestyle counseling	x	x	x	x	x	x
7-point glucose		x				x
Labs (HbA1c, lipids, CMP, Hb)	x				x	x
Dispense trial drug		x		x	x	
Hypoglycemia assessment	X	X	X	x	x	x
Frequency of glucose monitoring				x	x	x
Titrate insulin		x	x	x	x	
Liraglutide titration (if applicable)			x			
Insulin dose assessment		x	x	x	x	x
Compliance assessment				x	x	x
# daily injections				x	x	x
QoL questionnaires (DQOL and SF36)		x				x
AE and SAE assessment		x	x	x	x	x
Pregnancy test (if needed)	x	x		x	x	x
Physician time assessment		x	x	x	x	x

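### The primary HbA1c model names no adjustment for baseline HbA1c or the two stratification factors; adding them costs little power and may gain some, from none to substantial

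*Combined protocol and SAP*

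**What the plan says.** All references are to the combined protocol and SAP.

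- **Statistical Analysis Plan, primary analysis.** The estimand is the between-arm "group net difference (month 6 minus month 0) in" HbA1c. The 95% "confidence interval will be derived from the differences of least square means estimated" from a repeated-measures mixed model, and non-inferiority is concluded if its upper limit is below 0.4. No model terms are listed.
- **Same section, software paragraph.** SAS will be used, "particularly Proc Mixed for linear models with both fixed and random effects". The effects are not named, and the covariance structure is left for later assessment.
- **Same section, secondary analyses.** Baseline covariates appear once, in logistic models meant "to evaluate any association of baseline covariates on treatment efficacy". These do not adjust the primary comparison.
- **Randomization (visit 2), repeated in the Randomization section of Statistical Considerations.** The "statistician will generate a blocked randomization scheme (1:1) stratified by" insulin treatment at screening (yes/no) and BMI with a cut-off of 37. No analysis section carries these factors forward.
- **Which sample is month 0.** The Primary outcome runs from randomisation, and the visit table places time 0 at visit 2. Randomization (visit 2) adds: "At this visit we will obtain a full baseline evaluation of all outcome parameters". Yet the table row "Labs (HbA1c, lipids, CMP, Hb") is ticked only at visits 1, 5 and 6, and Assessments for Efficacy likewise lists screening, 3 months and 6 months. Under Screening Visit, blood will "be drawn (if not done within the past 7 days) to assess for all eligibility criteria (HbA1c and others), so a result up to 7 days old can stand in for the screening sample.

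**The concern.** A month 6 minus month 0 contrast taken from repeated-measures least-square means reads most naturally as a model with month 0 as one of the responses and arm means free at every visit. With complete data that contrast equals the simple difference in mean change. It uses baseline HbA1c with a fixed coefficient of one instead of the coefficient the data support, and it leaves any variation explained by the strata in the error term.

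What is at stake is the width of the interval that is set against 0.4. If the true SD of change is near the plan's planning value there is little to lose. If it is nearer the 0.7 that the plan also tabulates, power is 0.755 at 44 per arm, and precision left unused could decide the result. The model is also open: a change score, a baseline-adjusted model and a constrained-baseline model all fit the text and can give different upper limits.

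**Working it through.** **Inputs from Sample Size Calculation:** margin 0.4, true difference 0, one-sided alpha 0.025, 44 completers per arm, SD of change 0.5 (with 0.3 and 0.7 also tabulated), two-sample t-test without covariates.

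**Step 1: reproduce the plan.** Power is P(T > t(0.975, df)) for a non-central t with non-centrality 0.4/(SD × sqrt(2/n)) and df = 2n − 2.
- SD 0.5, 44/44: 0.960. The plan gives 0.960.
- SD 0.7, 44/44: 0.755. The plan gives 0.755.
- SD 0.7, 50/50: 0.808. The plan gives 0.808.

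**Step 2: effect of adjusting for baseline.** Let k be the month-6 SD divided by the baseline SD, and rho their correlation. The change score has variance proportional to 1 + k² − 2k·rho, and the baseline-adjusted residual to k²(1 − rho²). The ratio, adjusted to change score, is

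k²(1 − rho²) / (1 + k² − 2k·rho).

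It never exceeds 1, and equals 1 (no gain) when k·rho = 1. The documents give neither k nor rho, so both are assumed. Adjusted power uses SD × sqrt(ratio) with 3 degrees of freedom removed (baseline plus two binary strata).

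SD 0.7, 44/44, against 0.755 unadjusted:

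| k | rho 0.1 | rho 0.3 | rho 0.5 | rho 0.7 |
|---|---|---|---|---|
| 1 | 0.947 | 0.908 | 0.864 | 0.819 |
| 1.25 | 0.900 | 0.849 | 0.801 | 0.763 |
| 1.5 | 0.862 | 0.810 | 0.770 | 0.756 |
| 2 | 0.815 | 0.772 | 0.755 | 0.786 |

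Example, k = 1 and rho = 0.5: ratio 0.75/(2 − 1) = 0.75; residual SD 0.7 × sqrt(0.75) = 0.606; power 0.864.

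At SD 0.5 the same grid runs from 0.960 to 0.999, so the ceiling on the gain is 1 − 0.960 = 4 points. With k = 0.75 at SD 0.7, the four correlations give 0.988, 0.974, 0.957 and 0.943.

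**Step 3: effect of the strata.** Suppose strata balanced by arm explain a share f of the variance (assumed). The estimated difference then has true variance (1 − f) times what the unadjusted model reports. At a true difference of 0.4, the unadjusted false non-inferiority rate is about P(Z > 1.988/sqrt(1 − f)), where 1.988 is the t critical value on 86 df.
- f = 0.10: 1.988/0.949 = 2.095, giving about 0.018.
- f = 0.30: 1.988/0.837 = 2.376, giving about 0.009.

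Simulation gave 0.018 and 0.009 unadjusted, against 0.024 and 0.025 adjusted (nominal 0.025).

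Power at SD 0.7 with f = 0.10:
- Unadjusted: SE as reported is 0.7 × sqrt(2/44) = 0.149. The interval clears the margin when the estimate is below 0.4 − 1.988 × 0.149 = 0.103. The true SE is 0.149 × 0.949 = 0.142, giving about 0.767 (simulated 0.766).
- Adjusted: SD 0.7 × 0.949 = 0.664, giving about 0.797.

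The gain is about 3 points. The comparator is 0.766, not 0.755, because balanced prognostic strata help the unadjusted test too.

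**Step 4: cost if the covariates explain nothing beyond the change score.**
- Three degrees of freedom alone: 0.7550 to 0.7546 at SD 0.7.
- Adding chance imbalance in baseline HbA1c (variance × (1 + 1/84)): 0.750 at SD 0.7 and 0.958 at SD 0.5, a cost of about 0.5 and 0.2 points.
- If the strata are also unbalanced among completers (variance × (1 + 3/82) = 1.037): 0.740 at SD 0.7 and 0.954 at SD 0.5, a cost of about 1.5 and 0.6 points.

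**The case against.** The best defence is that the plan is coherent as it stands. It was sized with an unadjusted t-test on change, an unadjusted change analysis is valid, and power at the planning SD is already 0.960. The large gains need the SD 0.7 scenario together with a low correlation and similar SDs at the two visits, none of which the documents establish. All of that stands, and it limits the point to efficiency and pre-specification.

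The SD-ratio range of 1 to 2 is also only an assumption. Entry at HbA1c above 10% can narrow the baseline spread and push the ratio up. But the Inclusion Criteria set no upper limit and both arms titrate to glucose targets, so a ratio below 1, with a larger gain, is not excluded.

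A reader might infer stronger claims that the documents do not support:

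- *That the unadjusted interval risks a false claim of non-inferiority.* Step 3 shows that any departure from 0.025 is downward.
- *That the plan excludes adjustment.* It is silent.
- *That everything confirmatory hangs on this contrast.* Sample Size Calculation also powers the composite outcome for superiority, and Evaluability of Subjects describes a secondary analysis as confirmatory.
- *That the insulin stratum is defined in two conflicting ways.* The shorter wording in the later Randomization section, under Study Drugs and Materials, reads as shorthand and is an editorial matter.

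Practical doubt over month 0 is likewise small, since only one pre-treatment HbA1c is scheduled. The sections still need to agree.

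**Conclusion.** The point holds as a recommended improvement to the primary analysis. No section places baseline HbA1c or either stratification factor in the primary model, although all three are available before treatment starts. On the natural reading the result is valid but can be less precise than it need be, and conservative if the strata are prognostic.

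The size depends on quantities the documents do not give. At SD 0.5 it is at most 4 points of power. At SD 0.7 it runs from none to about 19 points (0.755 to 0.947) over the assumed ratios and correlations, and strata alone are worth about 3 points at an assumed 10% of variance. Against that, the worst-case cost at SD 0.7 is about 0.5 points, or about 1.5 if strata are unbalanced among completers. These figures assume complete data at 44 per arm and a true difference of zero.

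**What to change.** In the primary analysis paragraph of the Statistical Analysis Plan, specify a mixed model on HbA1c change at months 3 and 6 with treatment, visit, treatment-by-visit, baseline HbA1c, baseline-by-visit, insulin stratum and BMI stratum (the values used at randomisation), and an unstructured covariance. Compare the upper 95% limit of the adjusted month-6 difference with 0.4.

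State that baseline is the screening HbA1c, or the result from the preceding 7 days that Screening Visit accepts, since this is the only scheduled pre-treatment measurement. Reconcile that with the Primary outcome (which starts at randomisation), the full baseline promised at visit 2, and time 0 in the visit table. Align the insulin-stratum wording in the later Randomization section at the same time.

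The cost is a few sentences. Sample size, visits and data collection are unchanged.
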